- Study Design:** This is a multicenter, randomized, placebo-controlled, double-blind study to evaluate the safety and immunogenicity of a 2-injection vaccine regimen with the Chikungunya virus (CHIKV) virus-like particle vaccine (CHIKV VLP, VRC-CHKVLP059-00-VP) in healthy adults. The hypothesis is that the vaccine regimen is safe and induces a neutralizing antibody response to CHIKV. The primary objectives are to evaluate safety and tolerability of a 2-injection investigational vaccine regimen of VRC-CHKVLP059-00-VP at 20 mcg compared to placebo in healthy adults in CHIKV endemic areas. The secondary objective is to evaluate neutralizing antibody response in vaccine recipients. The exploratory objectives relate to assessing incidence of CHIKV infection in vaccine and placebo recipients, as well as antigen-specific humoral and cellular immune responses during the study.
- Product Description:** VRC-CHKVLP059-00-VP is an investigational VLP vaccine that consists of the E1, E2 and capsid proteins of CHIKV (strain 37997). VRC-PBSPLA043-00-VP is sterile phosphate-buffered saline (PBS) prepared for human injection as a placebo.
- Subjects:** Healthy adult subjects ages 18 to 60 years old that reside in CHIKV endemic regions.
- Study Plan:** 400 subjects stratified by age groups 18-40 and 41-60 years will be randomized in a 1:1 ratio to vaccine or placebo. Subjects will receive 2 intramuscular (IM) injections via needle and syringe per the study schedule below:

Group	Number of Subjects	VRC 704 Study Injection Schedule	
		Day 0	Day 28(+14)
1	200	20 mcg	20 mcg
2	200	PBS	PBS
All injections will be administered IM at 0.5 mL by needle and syringe.			

- Study Duration:** Subjects will be evaluated at 11 clinical visits during 72 weeks of study participation as follows: Day 0 and Weeks 4, 8, 16, 24, 32, 40, 48, 56, 64 and 72.

1. INTRODUCTION

The Dale and Betty Bumpers Vaccine Research Center (VRC), National Institute of Allergy and Infectious Diseases (NIAID), National Institutes of Health (NIH) (Bethesda, MD, USA) is dedicated to translating the latest knowledge of disease pathogenesis and immunology into new vaccine strategies to provide safe and effective means to prevent and control infectious diseases. Chikungunya virus (CHIKV) is a mosquito-borne disease causing acute infection associated with severe morbidity that can persist for several weeks, months or even years. Since its discovery in Tanzania in 1952, outbreaks of CHIKV have occurred most frequently in Africa, Asia and the Indian subcontinent. In recent decades, the disease has spread to Europe and the Americas. As of January 2015, over 1,135,000 suspected cases of CHIKV and 176 CHIKV-attributable deaths have been recorded in the Caribbean islands, Latin American countries and USA [1]. There are currently no effective vaccine or therapies against CHIKV. The rapid emergence of CHIKV supports the need for a safe and immunogenic vaccine. This protocol is designed as a Phase 2 evaluation of the investigational Chikungunya virus virus-like particle vaccine (CHIKV VLP), VRC-CHKVLP059-00-VP. This candidate vaccine was evaluated in a Phase 1 study as safe and well-tolerated and observed to induce neutralizing antibody responses at levels hypothesized to be protective against CHIKV infection [2].

1.1. Chikungunya: Etiology, Disease Course and Epidemiology

CHIKV (genus *Alphavirus*, family *Togaviridae*) is an arthropod-borne viral disease with a positive, 11.8 kilobase (kb) single-stranded RNA genome encoding structural and non-structural proteins [3, 4]. The virus has three distinct clades that share a high percentage of amino acid similarity: West African, Central/East/South African, and Asian genotypes [5-7].

Initial case reports of CHIKV refer to an outbreak in Tanzania in 1952-53 [8, 9] and early outbreaks were geographically limited [10]. Prior to 2013, CHIKV outbreaks were primarily detected in regions of Africa, Asia, Europe, and the Indian and Pacific Oceans. Late in 2013, the first local transmission of CHIKV was reported in the Americas [11-14]. The virus is transmitted through infected mosquitoes, predominantly *Aedes aegypti*, in sylvatic and human-mosquito-human cycles [12, 13]. Genetic mutations in viral genome have enabled virus transmission through a new host, *Aedes albopictus*, altering CHIKV epidemiology and driving outbreaks in new regions [15-17].

CHIKV infection is associated with severe morbidity lasting 1-2 weeks, with symptoms persisting for weeks to months. The incubation period lasts 2-12 days [18]. Acute clinical manifestation involves high fever, rash, gastrointestinal complications, conjunctivitis, headache, arthralgia, nausea, fatigue and myalgia. The hallmark symptom of the infection, debilitating polyarthralgia/arthritis, is present in nearly all cases (>70%) [11, 18, 19]. Onset of alphavirus-associated arthritis begins within 2-5 days after the infecting mosquito bite, coinciding with presence of virus by polymerase chain reaction (PCR) and innate immune responses against circulating virus. The timing and onset of arthritis is not consistent with adaptive immune responses that occur around day 7-14. Persistent arthritis (3-13% of cases) has been associated with pro-inflammatory cytokines and detectable virus in the joint fluid and cells [20-23]. CHIKV-associated mortality is low; the majority of fatal cases occur in older populations with underlying medical conditions [1, 24]. Though atypical, neurological complications including encephalitis and meningoencephalitis have been seen in a growing number of cases [11, 25, 26].

There is currently no vaccine or anti-viral therapy available for the prevention or treatment of CHIKV infection. The economic losses and added stress on public health infrastructure experienced in areas of CHIKV outbreaks along with heightened potential for global spread necessitate vaccine development as a high global priority [2, 10, 27].

1.2. Rationale for Development of VRC-CHKVLP059-00-VP

CHIKV strains have high amino acid sequence homology and are antigenically related; therefore, it is possible to design a vaccine that could be cross-protective against heterologous strains [7, 27-29]. Infection with CHIKV induces long-lasting protective immunity. Both humoral and cellular immunity are detected in survivors of CHIKV infection, however, their relative contribution to protection is unknown [21].

Recent changes in the epidemiology and pathogenicity of circulating CHIKV strains prompted close attention to genetic changes in the virus [15, 16, 30] and to viral immunobiology [21, 31-33]. It was noted that persistent chronic inflammation and incapacitating arthralgia/arthritis could be observed in some infected patients for months despite a robust immune response [21]. Comprehensive study of the production of cytokines, chemokines and growth factors during acute CHIKV infection revealed a predominance of type 2 circulating cytokines, and that increase in interleukin (IL)-1 β , IL-6 and decrease in RANTES (regulated upon activation, normal T-cell expressed and secreted) expression were associated with disease severity [33].

Development of a preventive CHIKV vaccine began in the early 1970s with investigation of inactivated vaccine candidates [34, 35]. Formalin-inactivated vaccine was tested in a small group of volunteers and reported to be safe and immunogenic [34]. Subsequently, a live-attenuated vaccine candidate was developed and progressed into Phase 2 clinical trials. The attenuated vaccine induced neutralizing antibody by day 28 in 98% of evaluable vaccinees (n=57), which persisted at least 12 months in 85% of vaccinees. The vaccine was assessed as safe and well-tolerated; reactogenicity reports included transient arthralgia without arthritic signs in 8% of vaccinees [36]. Immunologic interference was revealed in sequential administration of live attenuated alphavirus vaccines [37]. Additional CHIKV vaccination strategies in preclinical and clinical stages include a chimeric alphavirus vaccine candidate, recombinant measles-virus-based CHIKV vaccine, and a consensus-based DNA vaccine candidate [38-40].

The VRC has developed a CHIKV virus-like particle (VLP) candidate vaccine [2, 27]. VLPs are multi-protein structures that mimic the organization and conformation of viruses but lack the viral genome [41]. Compared to inactivated subunit vaccines, VLPs present conformational viral epitopes similar to the authentic virus [42]. VLPs are considered highly immunogenic and are known to elicit high neutralizing antibody titers with good durability [43-45]. The FDA has approved several prophylactic VLP vaccines including hepatitis B vaccines (Engerix[®] and Recombivax HB[®], GlaxoSmithKline and Merck, respectively) and human papilloma virus (HPV) vaccines (Cervarix[®] and Gardasil[®], GlaxoSmithKline and Merck, respectively). Several other VLP vaccine candidates, such as vaccines for influenza, Norwalk and parvovirus, are in pre-clinical testing or Phase 1 studies [41, 42].

Selective expression of the CHIKV structural proteins in mammalian cells results in formation of VLPs that resemble replication-competent alphavirus particles [27]. Immunization with CHIKV VLPs induced antibodies against envelope proteins that neutralized virus *in vitro* and protected against a systemic live virus challenge in non-human primates (NHP). Purified IgG from the

CHIKV VLP-immunized monkeys protected immune-deficient mice from a lethal virus challenge, suggesting that antibodies are an important component of a protective immune response. Preclinical animal studies demonstrate that the VLP vaccine candidate, VRC-CHKVLP059-00-VP, has the potential to elicit protective immunity in humans.

1.3. Previous Human Experience with VRC-CHKVLP059-00-VP

VRC-CHKVLP059-00-VP was assessed under VRC 311 (2011-2012), a Phase 1 open-label, dose-escalation study to evaluate safety and immunogenicity of the vaccine. Twenty-five (25) adults, 18-50 years old, received three intramuscular (IM) injections on weeks 0, 4, and 20 via needle and syringe in doses of 10 mcg (n=5), 20 mcg (n=10), or 40 mcg (n=10).

All injections were well tolerated with no reported arthralgia or fever after vaccination and no serious adverse events (SAEs). Solicited reactogenicity parameters were either none or mild; 36% of vaccinees (n=25) reported mild local reactogenicity and 40% reported mild systemic reactogenicity at least once following vaccination [2]. Neutralizing antibodies were detected in all subjects by 4 weeks after the second vaccination. A significant boost occurred after the third vaccination in all dose groups. Neutralization titers of vaccine recipients reached levels comparable to those reported after natural infection, suggesting a potentially durable protective response to the vaccine [2]. The study detected antibodies by ELISA in 80-100% of subjects in all three dose groups and geometric mean titers (GMT) were not significantly different between the groups except at week 24. The study also found no significant difference in group GMT 4 weeks after the second dose compared to 4 weeks after the third dose.

1.4. Rationale for Study Agent Dose and Schedule

Based on VRC 311 study results that all three dose levels (10 mcg, 20 mcg, and 40 mcg) were safe and well tolerated [2] and all dose levels elicited robust titers of CHIKV neutralizing antibodies as well as durable, vaccine-induced antibodies that persisted through to the final study visit 6 months after the last dose, VRC-CHKVLP059-00-VP will be evaluated in a 2-injection schedule at a dose of 20 mcg. Gaining early information about frequency, magnitude and durability of response to a schedule with two vaccinations will be informative to designing future Phase 3 efficacy studies.

1.5. Assessment of Immunogenicity

In protocol VRC 704, specimens to evaluate immunogenicity will be taken at baseline and at specified time points. The primary immunogenicity timepoint is 4 weeks after the second injection. Measurements of CHIKV-specific humoral immune responses will be assessed by neutralization antibody (NAb) assays [2].

ELISA and other exploratory assays to assess for humoral and cellular immune responses may be performed with stored samples, depending upon the most efficient use of laboratory resources to inform product development. Human leukocyte antigen (HLA) type may be obtained from stored samples if needed to assess HLA-class restricted cellular responses.

Research samples for immunogenicity assays will be processed by the NIAID Vaccine Immune T Cell and Antibody Laboratory (NVITAL) in Gaithersburg, MD, where many of the immunogenicity assays will also be performed. Immunogenicity assays may be performed by VRC laboratories in Bethesda, MD, contract laboratories, or by other research collaborators.

2. STUDY AGENTS

Study agents are manufactured under Good Manufacturing Practice.

2.1. VRC-CHKVLP059-00-VP Study Agent

VRC-CHKVLP059-00-VP is a VLP vaccine that consists of CHIKV VLPs composed of the E1, E2, and capsid proteins of the CHIKV (strain 37997). VLPs are produced in the VRC293 cells using a transient expression system. The production process consists of upstream production (cell growth and antigen expression) and downstream purification. In the first step, VRC293 cells are expanded from the working cell bank until the desired number of cells is obtained. Cells are then transfected with the expression plasmid VRC8900 that encodes for CHIKV structural proteins (capsid, E3, E2, 6K, and E1). The 6K and E3 proteins have not been specifically detected in the VLPs of the VRC-CHKVLP059-00-VP candidate. VLPs are produced as the secreted product, harvested and clarified; this culture medium is used as the starting material for the downstream purification process. Purification includes tangential flow filtration, Q-Sepharose column chromatography, diafiltration, and sterile filtration. Enveloped VLPs self-assemble and are released into the culture medium as ~65 nm particles. No replication-competent viral genetic material is incorporated in the VLP. After purification, the VLPs are diluted into a sucrose-containing citrate buffer, sterile-filtered, filled into single-dose glass vials, and stoppered to produce drug product.

CHIKV VLP drug product is a sterile aqueous buffered solution of CHIKV VLP drug substance filled into single dose glass vials at 40 ± 10 mcg/mL. The composition of drug product is presented in [Table 1](#). Vials have a nominal fill of 0.8 mL to allow withdrawal of 0.5 mL. More details related to vaccine preparation, quality control and preclinical studies performed before the candidate vaccine entered Phase 1 study can be found in the Investigator's Brochure.

Table 1: Quantitative Composition of the VRC-CHKVLP059-00-VP

Ingredient	Composition (per 1.0 mL)	Function
Active Substance		
CHIKV VLP	40 mcg	Antigen
Excipients		
Sucrose	74.6 mg	Buffer component
Potassium phosphate (monobasic)	0.5 mg	Buffer component
Potassium phosphate (dibasic)	1.1 mg	Buffer component
Sodium citrate (dihydrate)	7.4 mg	Buffer component

2.2. VRC-PBSPLA043-00-VP as Placebo

VRC-PBSPLA043-00-VP, a sterile phosphate buffered saline (PBS) is the placebo for the CHIKV VLP vaccine.

3. STUDY OBJECTIVES

3.1. Primary Objective:

- To evaluate the safety and tolerability of VRC-CHKVLP059-00-VP in healthy adults that reside in CHIKV endemic areas when administered intramuscularly by needle and syringe at a dose of 20 mcg compared to placebo.

3.2. Secondary Objectives:

- To evaluate the immune response to VRC-CHKVLP059-00-VP by neutralization assay at 4 weeks after the second 20 mcg dose (Study Week 8).

3.3. Exploratory Objectives:

- To evaluate humoral and cellular responses to VRC-CHKVLP059-00-VP at additional time points. CHIKV-specific responses will be assessed by antibody assays that include antigen-specific ELISA and neutralization assay.
- To compare incidence rates of CHIKV infection in vaccine and placebo recipients.
- Clinical and virus characteristics of infections will also be compared in vaccine and placebo recipients.

4. STUDY DESIGN AND CLINICAL PROCEDURES

This is a Phase 2 multicenter, randomized, placebo-controlled, double-blind study to examine the safety and immunogenicity of a 2-injection vaccine regimen (Day 0 and 28) with the CHIKV VLP vaccine or PBS placebo in healthy adults. The hypothesis is that the vaccine regimen is safe and induces a neutralizing antibody response to CHIKV. The study schema is shown in [Table 2](#) below. The expected duration of time on the study per subject is approximately 72 weeks.

Table 2: Study Schema

Group	Number of Subjects	VRC 704 Study Injection Schedule	
		Day 0	Day 28(+14)
1	200	20 mcg	20 mcg
2	200	PBS	PBS
All injections will be administered IM at 0.5 mL by needle and syringe.			

4.1. Study Population

The study is designed for the enrollment of healthy adults. The following eligibility criteria will be used.

4.1.1. Inclusion Criteria

A subject must meet all of the following criteria:

1. 18 to 60 years old
2. Available for clinical follow-up through Study Week 72
3. Able to provide proof of identity to the satisfaction of the study clinician completing the enrollment process
4. Able and willing to complete the informed consent process
5. Willing to donate blood for sample storage to be used for future research
6. In good general health, with a BMI ≤ 40 , without clinically significant medical history, and has satisfactorily completed screening
7. Physical examination and laboratory results without clinically significant findings within the 56 days prior to enrollment

Laboratory Criteria within 56 days prior to enrollment:

8. Hemoglobin either within institutional normal limits or accompanied by site physician approval as consistent with healthy adult status
9. White blood cells either within institutional normal range or accompanied by site physician approval as consistent with healthy adult status
10. Platelets = 125,000 – 500,000/mm³
11. Alanine aminotransferase (ALT) ≤ 1.25 x upper limit of normal (ULN)
12. Serum creatinine ≤ 1.1 x ULN based on site institutional normal range
13. Negative result on an HIV test that meets local standards for identification of HIV infection
14. Negative result on the CHIKV screening antibody assay.

Criteria applicable to women of childbearing potential:

15. Negative human chorionic gonadotropin pregnancy test (urine or serum) on day of enrollment
16. Agree to use an effective means of birth control from 21 days prior to enrollment through 12 weeks after the last study injection

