4.2.2. Screening Visit(s)

Screening for this study may be completed through a general screening protocol after signing a site-specific IRB-approved consent form to be screened or through screening consent language incorporated into the VRC 704-specific consent form. A screening segment for the study will be included in data collection to provide information on reasons for non-enrollment to begin study injections. Evaluations will be done according to eligibility criteria and clinical assessment at screening. Screening evaluations for specific eligibility criteria must be completed within the time interval specified prior to enrollment, but may be repeated as needed to confirm eligibility. Samples collected during screening may be used for assay validation and site proficiency testing.

The Assessment of Understanding (AoU) is a tool to help staff identify topics which may not be fully understood by study volunteers. As part of the screening process, the AoU should be completed and incorrect answers discussed with the subject. The AoU may be performed one time or more than one time as needed with a given subject. The timing of when to conduct the AoU is adaptable to the practices that work best for each clinical site, however it must be done within the time frame starting after initiation of screening until just prior to or during enrollment (prior to vaccination) on Day 0. Each site is encouraged to develop a site standard among their own staff for consistency of site practices in the conduct of the consent process and deployment of the AoU as part of the consent process. A subject may be re-screened prior to enrollment if there is a suspected change in health status.

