APPENDIX III: SCHEDULE OF EVALUATIONS

VRC 704 Schedule of Evaluations														
Visit	01	02	02A	03	03A	04	05	06	07	08	09	10	11	12
Week of Study	-8 to 0	W0	W1	W4	W5	W8	W16	W24	W32	W40	W48	W56	W64	W72
Day of Study	-56 to 0	D0 ¹	D7	D28	D35	D56	D112	D168	D224	D280	D336	D392	D448	D504
Clinical Evaluations														
² Informed Consent, AoU	X													
³ Targeted physical exam	X	[X]		[X]		[X]								
Targeted medical history; vital signs	X	X	X	X	X	X	X	X	X	X	X	X	X	X
⁴ Study Injections		X		X ⁵										
Begin 7-Day Diary Card		X		X										
Phone contact; clinic visit if indicated			X		X									
Counseling on pregnancy prevention		X		X		X								
CBC, differential, platelets				3	3	3								
⁶ Pregnancy test: urine (or serum)		X	X	X			X							
ALT		4	4	4		4								
HIV ⁷ , creatinine		4												
Research Immunology														
Antibody assays and serum		40		40		40	40	40	40	40	40	40	40	40
⁹ Serum for diagnostic testing				[X]		[X]								
⁹ Plasma for diagnostic testing				[X]		[X]								
¹⁰ PBMC and plasma		[40]		[40]										[40]
Daily Volume (mL)	27	87	-	87	-	47	40	80						
Cumulative Volume estimate (mL)	27	114	-	201	-	248	288	328	368	408	448	488	528	608

¹ Day 0=day of enrollment and (blinded) CHIKV VLP vaccine or PBS injection. Day 0 evaluations prior to first injection are the baseline for assessing adverse events subsequently. Schedule Visits 02A through 04 with respect to the last prior injection day and subsequent visits with respect to Day 0. The visit windows are: Visits 02A and 03A (+3 days); Visit 03 (+14 days); Visit 04 (±7 days); Visits 05 through 12 (±21 days).

² Screening evaluations may be repeated or completed over more than one visit, if needed. Screening research blood draw and consent obtained more than 56 days prior to enrollment are not required to be repeated.

³ Screening physical exam is targeted to eligibility and includes height/weight; the [X] at other visits indicates targeted exam only if needed based on interim history.

⁴ Safety and research blood and vital signs must be collected before study injections are administered. Complete BP, pulse and injection site assessment at 15 minutes or later after study injection before subject leaves the clinic.

⁵ The preferred window for the second injection is +14 days. The injection may occur outside the preferred window with approval by the Protocol Chair.

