6.3 Analysis Populations

The **Safety** population will include all enrolled subjects, summarized according to the actual vaccination received.

The **Per Protocol (PP)** analyses will include all subjects receiving two injections within window as assigned by the randomization schedule, and not experiencing any other major protocol deviations prior to their week 8 visit. Major protocol deviations include ineligibility, product administration deviations, and primary endpoint missing data. The subjects will be analyzed based on product actually received, regardless of randomization assignment. If subjects receive study vaccine for one visit and placebo for the other, then they will be included in the PP population until they receive the second injection or are otherwise removed from the PP population. The PP analyses will also include subjects determined to be CHIKV infected prior to the receipt of their scheduled second injection and not experiencing any other major protocol deviations prior to their state of infection. Subjects will be censored from the immunogenicity analysis following PCR-confirmed CHIKV infection. Immunogenicity and infection rates will both be examined for the PP population.

The **Intent-to-treat (ITT)** population will include all enrolled subjects, analyzed according to the randomized treatment. The ITT population will be used to analyze immunogenicity and infection rates.

The **Modified intent-to-treat (mITT)** analyses will include all enrolled subjects that received at least one product administration with non-missing immunogenicity data at their Week 8 visit, analyzed according to the study product(s) received. This definition will exclude subjects with protocol deviations related to possible dosing errors. The mITT population will only be used for immunogenicity analyses.

Subjects excluded from Immunogenicity (or CHIKV Incidence) analyses are listed in Appendix III, **Listing 16.2.3**.

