9 IMMUNOGENICITY EVALUATION

Specimens to evaluate immunogenicity will be taken at baseline and at specified time points. The primary immunogenicity timepoint is 4 weeks after the second injection. Measurements of CHIKV-specific humoral immune responses will be assessed by neutralization antibody (NAb) assays. A listing of individual titer levels and the corresponding planned and actual collection dates are presented in **Appendix III, Listing 16.2.6**.

At some sites, positive baseline Week 0 neutralization antibody assay results were reported. ELISA response data, captured as part of the screening eligibility process, have been received by the Sponsor from the laboratory. When raw ELISA data is received, baseline ELISA responses will be assessed in relation to neutralization antibody data and results will be reported. For further information, a separate analysis plan will be created to elaborate on specific analyses to be performed.

The principle immunogenicity endpoint is measured at Week 8 by neutralization assay.

Descriptive analyses will be presented by study day, age group, and treatment group, aggregated over all study sites and by site. If none or a very small number of placebo group subjects have a neutralization response, their results will only be reported for the positive response rate summaries and omitted from other analyses. This approach is taken to achieve brevity and easier understanding of results when the control group has no meaningful responses.

Summaries include:

- GMT and their confidence intervals (**Table 14.2.1, Appendix I**)
- Geometric mean ratio (GMR) of results obtained at baseline (Week 0) to results obtained at Week 8 and its 95% CI. (**Table 14.2.1, Appendix I**)
- Positive response rates, as defined by an assay-specific post dose response, and their exact 95% CI (**Table 14.2.1, Appendix I**)
- Reverse cumulative distribution of the neutralization assay results (**Figure 14.2.1, Appendix II**)
- Boxplots of titer values (**Figure 14.2.2, Appendix II**).

These summaries will be repeated for all exploratory research tests used to measure exploratory immunogenicity endpoints at the timepoints for which there are data.

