Pulse	Normal													
	Mild													
	Moderate													
	Severe													
	Potentially Life Threatening													
Temperature (°C)	Normal													
	Mild													
	Moderate													
	Severe													
	Potentially Life Threatening													

TABLE 14.3.6:
Number and Percentage of Subjects with Concurrent Medications by
Treatment Group <<Age Stratum>>

Medication	CHIKV (N=X)		Placebo (N=X)		All Subjects (N=X)	
	n	%	n	%	n	%
	x	x.x	x	x.x	x	x.x

TABLE 14.3.7:
Number of Pregnancies by Outcome and Treatment Group

	CHIKV (N=X)	Placebo (N=X)	All Subjects (N=X)
Total pregnancies	x	x	x
Live births			
Spontaneous abortions			
Elective abortions			
Ectopic pregnancies			
Stillbirths			

TABLE 15.1.1:
Incidence of Clinical Cases of CHIKV Post Dose One by Treatment Group and Stratified by Age

Age Stratum	CHIKV			Placebo		
	n	%	95%CI	n	%	95%CI
18-40	x	xx	xx-xx	x	xx	xx-xx
41-60						
Aggregate (18-60)						

Note: Subjects not receiving dose two are included in this table.
 n = number of subjects with CHIKV symptoms (clinical cases)
 % = n divided by the number of subjects receiving dose one
 95%CI = 95% Clopper-Pearson confidence interval.

TABLE 15.1.2:
Incidence of Clinical Cases of CHIKV Post Dose Two by Treatment Group and Stratified by Age

Age Stratum	CHIKV			Placebo		
	n	%	95%CI	n	%	95%CI
18-40	x	xx	xx-xx	x	xx	xx-xx
41-60						
Aggregate (18-60)						

n = number of subjects with CHIKV symptoms (clinical cases)

% = n divided by the number of subjects receiving dose two and free of infection when receiving dose two

95%CI = 95% Clopper-Pearson confidence interval.

Additional Tables using the same format as 15.1.1 and 15.1.2

TABLE 15.1.3:
Incidence of PCR Confirmed Cases of CHIKV Post Dose One by Group and Stratified by Age

TABLE 15.1.4:
Incidence of PCR Confirmed Cases of CHIKV Post Dose Two by Group and Stratified by Age

TABLE 15.2.1:

Primary Exploratory Analysis – Vaccine Efficacy for Time to Occurrence of Clinical CHIKV Infection Post Dose One

	CHIKV N= Placebo N=		
	V.E.	95% CI for V.E.	p-value
Primary Analysis: Unadjusted	x.xx	xx.xx - xx.xx	x.xxx

N=number of subjects in the specific treatment group that received first dose

V.E. =Vaccine efficacy obtained from Cox Proportional Hazard model

95%CI = 95% confidence interval obtained from Cox Proportional Hazard model

p-value = result of comparison of Kaplan-Meier survival curves between groups by Log-rank test.

TABLE 15.2.2:

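### No infection analysis or per-protocol rule uses the Day 0 titre, although some were positive, so PCR-confirmed incidence per susceptible adult is understated by the share immune at Day 0

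*Combined protocol and SAP*

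**What the plan says.** Protocol 4.1.1 requires a "Negative result on the CHIKV screening antibody assay" and lists it under "Laboratory Criteria within 56 days prior to enrollment". Protocol 4.2.3 lets an in-window screening result stand at enrollment, and no text makes the Day 0 titre a condition of entry.

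SAP section 9 then reports: "At some sites, positive baseline Week 0 neutralization antibody assay results were reported". It gives no count. It plans to set baseline ELISA results against the neutralization data and leaves the details to a separate plan.

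SAP 6.3 defines the per-protocol set: "Major protocol deviations include ineligibility, product administration deviations, and primary endpoint missing data". It says that immunogenicity and infection rates will both be looked at in that set. SAP section 10 runs efficacy in ITT, and the Table 14.1.2 shell allows no exclusions from ITT for infection rates. The Table 15.1.1 footnote defines the percentage as "n divided by the number of subjects receiving dose one". The Table 15.1.2 denominator is dose-two recipients who were uninfected at that dose. SAP 10.2 removes subjects with CHIKV before dose two from the post-dose-2 analysis. The adjusted efficacy shells (Tables 15.3.x) use age, race and site.

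On natural immunity, protocol 1.2 states: "Infection with CHIKV induces long-lasting protective immunity".

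**The concern.** The SAP treats infection before the start of an at-risk period in two ways. Someone who becomes a case between the doses is taken out of the post-dose-2 analysis. Someone whose serology points to infection before dose one stays in both analyses, because nothing in the infection or per-protocol rules looks at the Day 0 titre.

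This matters because protocol 6.3 names trustworthy incidence figures as a particular reason for the trial's size, for use in planning Phase 3. A denominator that includes people who are already protected gives a lower rate than a susceptible person would face. Since the positives arose at some sites, the shortfall may also differ between sites. The trial holds the data to show this, but no planned infection table does.

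**Working it through.** **1. Where the Day 0 titre is used.** It enters the immunogenicity summaries as the baseline GMT and in the geometric mean ratio. It does not enter the ITT or per-protocol definitions, the denominators of Tables 15.1.1-15.1.4, the Cox and log-rank analyses of Tables 15.2.1-15.2.4, or the covariates of Tables 15.3.x. A subject who was negative at screening and positive at Day 0 has met criterion 14 as written, so the ineligibility ground in SAP 6.3 does not remove that subject.

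**2. The nearest figure in the plan.** The documents state no incidence, efficacy power or baseline seropositivity. The closest figure is the chance of at least one event (protocol Table 3, SAP Table 2); CHIKV infection is a listed safety parameter.

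- n = 200 × (1 − 0.10) = 180
- 1 − (1 − 0.01)^180 = 83.62%, as stated

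**3. Effect on PCR-confirmed incidence.** Let s be the share immune at Day 0 and I the incidence among susceptible subjects. If immune subjects cannot become PCR-confirmed cases:

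- observed incidence = (1 − s) × I
- relative understatement = s
- correction factor = 1/(1 − s)

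| s (assumed) | Observed when I = 5% | Correction factor | Chance of ≥1 event in 180 when I = 1% |
|---|---|---|---|
| 0 | 5.00% | 1.00 | 83.62% |
| 5% | 4.75% | 1.05 | 82.06% |
| 10% | 4.50% | 1.11 | 80.35% |
| 20% | 4.00% | 1.25 | 76.44% |

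Two sites with the same 5% rate among susceptibles would show 5.0% and 4.0% if s were 0 at one and 20% at the other.

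**4. How s could arise (all inputs assumed).**

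- Infection between screening and Day 0: 1 − (1 − a)^(56/365) for an annual attack rate a. For a = 5%, 10% or 20% this is 0.78%, 1.60% or 3.37%, or about 3, 6 or 13 of 400. These are upper bounds, since they give everyone the full 56 days.
- A false-negative screen (specificity 1): the share of enrolled subjects is p(1 − Se)/[p(1 − Se) + 1 − p] for seroprevalence p and sensitivity Se. With p = 30% and Se = 95% it is 0.015/0.715 = 2.1%. With p = 50% and Se = 80% it is 0.10/0.60 = 16.7%.

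The 56-day gap is probably the smaller source.

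**5. Effect on relative efficacy.** Assume 200 per arm, 5% incidence in susceptible placebo subjects, 60% efficacy and the same s in both arms. The factor (1 − s) cancels: RR = (1 − s) × 2% / [(1 − s) × 5%] = 0.40. The 95% interval for efficacy is 1 − exp(ln RR ± 1.96 × SE), with SE² = (1 − p1)/(n × p1) + (1 − p0)/(n × p0).

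- s = 0: expected cases 4 and 10; SE² = 0.98/4 + 0.95/10 = 0.340; interval −25% to 87%.
- s = 20%: expected cases 3.2 and 8; SE² = 0.984/3.2 + 0.96/8 = 0.4275; interval −44% to 89%.
- s = 20%, analysed in the 160 susceptible subjects per arm: the same 3.2 and 8 cases; SE² = 0.98/3.2 + 0.95/8 = 0.425; interval again −44% to 89%.

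Restricting the analysis therefore corrects the incidence but does not win back the precision.

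**The case against.** Several objections stand and limit the point.

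- **Case definition.** SAP section 10 also counts illness consistent with CHIKV without PCR confirmation. An immune subject with another febrile illness can be such a case, so (1 − s) does not describe Tables 15.1.1-15.1.2 or 15.2.1-15.2.2. It applies to the PCR-confirmed tables.
- **Choice of rate.** Protocol 6.3 speaks of the target population. If a later trial screened in the same way, the as-enrolled rate would be a fair planning figure. That is a reason to show both rates, not to replace one.
- **Protection.** Protocol 1.2 adds that the shares of antibody and cellular immunity in protection are not known. In SAP 3.3 a titre of 30 is a response threshold and the assay's lower limit of confidence, not a correlate of protection.
- **Standing.** The infection analyses are exploratory and unpowered. Primary safety is untouched.
- **The separate plan.** It is not among these documents and might cover this. SAP section 9 describes it only as ELISA against neutralization work, so it cannot be relied on to do so.

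Three stronger readings are tempting but not supported.

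- **Biased efficacy.** A reader might infer that Day 0 immunity confounds the vaccine comparison. Randomization is 1:1 within site and age stratum, so any imbalance is chance, and the secondary analysis adjusts for site.
- **Retesting until negative.** Protocol 4.2.2 says that screening evaluations are to be done in their window, "but may be repeated as needed to confirm eligibility". A reader might infer that a later negative can cancel a positive. No text says so, and a repeat may simply refresh an old result. The Table 14.1.1 note, though only a reporting rule, counts a positive or indeterminate result on either the IgG or IgM test.
- **Exemption from the time limit.** Footnote 2 of protocol Appendix III reads: "Screening research blood draw and consent obtained more than 56 days prior to enrollment are not required to be repeated". A reader might infer that the CHIKV serology can be older than 56 days. The footnote concerns the research draw, and nothing shows that the eligibility serology comes from it.

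**Conclusion.** The point holds for PCR-confirmed incidence per susceptible adult, which is understated by a relative s: 5%, 10% or 20% for s = 5%, 10% or 20%. The direction follows once s is above zero and Day 0 positives are protected. SAP section 9 supports the first condition and protocol 1.2 the second, with a titre of 30 or more taken as protection by assumption. The size is unknown because the number of Day 0 positives is not given.

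The rate among subjects as enrolled is correct for that population. Relative efficacy is not biased in expectation; it loses precision. Nor are the Day 0 positives ineligible: they met criterion 14, and the sites that enrolled them on a negative screen followed the protocol. The gap lies in the analysis plan, and it should be closed because the incidence figure is meant to guide Phase 3.

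**What to change.** 1. In SAP 6.3, define a Day 0 NAb-negative set: Week 0 titre below 30, the SAP's own positivity value.
2. Report the number of subjects at or above 30 on Day 0 by site and arm.
3. Repeat Tables 15.1.1-15.1.4 and 15.2.1-15.2.4 in that set beside ITT. The PCR-confirmed tables matter most. Keep ITT as planned.
4. Add a per-protocol sensitivity analysis without Day 0 positives. Do not reclassify them as ineligible, which would create eligibility deviations where there were none.

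The Week 0 titre is already an endpoint measurement and the table shells exist, so the cost is some SAP wording and repeat runs. The added analyses will have fewer subjects. Changing the screening rules would not help this trial: the SAP already reports Week 0 results, and enrollment was planned to finish within 8 months of opening.
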